9.6.3 Laboratory Test Results

Summary statistics over scheduled visits for actual values, changes from baseline of laboratory parameters listed below will be presented. In addition, shift tables will be summarized with toxicity grades using CTCAE by worst on-study increase and decrease values between study baseline and any visit up to the end of the study. The schedule of assessments is pre-specified in Table 4 of protocol amendment 3 dated July 18, 2018.

1. Corrected Calcium
2. Magnesium
3. Total bilirubin
4. Direct bilirubin
5. Alkaline phosphatase
6. AST (SGOT)
7. ALT (SGPT)
8. Hemoglobin
9. Platelets
10. Neutrophils
11. Lymphocytes
12. LDH
13. Amylase
14. Lipase
15. Immunoglobulins (IgG, IgA, IgM),
16. Creatinine increased.

9.6.4 Vital Signs

Vital signs (systolic blood pressure, diastolic blood pressure, heart rate, respiratory rate and temperature) will be summarized at pre-specified times during treatment and at the safety follow-up (30 days after treatment). Changes from baseline and percent change will also be calculated. Additionally, summaries of the subject incidence with notable abnormalities defined in [Appendix A, Table 14-2](#) in Full Analysis Set will be presented.

9.6.5 Physical Measurements

Weight will be summarized at pre-specified times during treatment and at the safety follow-up (30 days after treatment). Changes from baseline and percent change will also be calculated. Additionally, summaries of the subject incidence with notable abnormalities defined in [Appendix A, Table 14-2](#) in Full Analysis Set will be presented.

9.6.6 Electrocardiogram

The electrocardiogram (ECG) measurements from this clinical study were performed as per standard of care for routine safety monitoring, rather than for purposes of assessment of potential QT interval corrected (QTc) effect. Because these evaluations may not necessarily be performed under the rigorous conditions expected to lead to meaningful evaluation of QTc data; neither summaries nor statistical analyses will be provided, and these data would not be expected to be useful for meta-analysis with data from other trials.

9.6.7 Antibody Formation

The incidence and percentage of subjects who develop anti-blinatumomab antibodies (binding and if positive, neutralizing) will be summarized and listed at each time point collected in Full Analysis Set. ,

9.6.8 Exposure to Investigational Product

Descriptive statistics will be produced to describe the exposure to blinatumomab for subjects in the Full Analysis Set. The number of days on IP and the proportion of subjects receiving each dose level will be summarized. In addition, the duration of therapy, the relative treatment duration, the cumulative dose, and the percent of intended dose will be summarized. The number and percent of subjects with dose modifications (eg, dose changes, dose interruptions) and reason for modification will be summarized.

9.6.9 Exposure to Other Protocol-required Therapy

Descriptive statistics will be produced to describe the required pre-medication (dexamethasone) exposure in the pre-treatment analysis set.”

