This is a phase 2, multicenter, open-label, single arm estimation study in adult subjects with high-risk DLBCL in complete remission. The study will consist of up to a **28**-day screening period, a run-in period of up to 24 months, a 12-week treatment period (8 weeks of blinatumomab treatment followed by a 4-week treatment free period), a 30-day safety follow-up visit after the last dose of blinatumomab, and a long-term follow-up period that begins after the safety follow-up visit is completed until 1 year from the first dose of blinatumomab. The study will enroll approximately 90 subjects in the screening period with biopsy proven, high-risk DLBCL that are positron emission tomography-computer tomography (PET-CT) negative 90 days (\pm 30 days) post aHSCT. During the run-in period subjects will be followed by clinic visits at regular interval for up to 24 months for monitoring of MRD status in plasma by a next generation sequencing (NGS)-based assay. It is estimated 30 subjects will be either MRD-positive at screening or become MRD-positive during the 24-month run-in period. The number of subjects enrolled may be altered in order to ensure that approximately 30 subjects are assigned to treatment with blinatumomab. Enrollment may be stopped, once approximately 30 subjects have been assigned to treatment with blinatumomab.

Sample Size: Approximately 90 subjects will be enrolled in the study and approximately 30 subjects will be assigned to treatment with blinatumomab.

Summary of Subject Eligibility Criteria: The study will enroll subjects age \geq 18 years with refractory or relapsed biopsy-proven high-risk DLBCL (excluding DLBCL that represents transformation of indolent Non-Hodgkin's Lymphoma (NHL). Subjects must have received aHSCT, be PET-CT negative at 90 days post-aHSCT, have an Eastern Cooperative Oncology Group (ECOG) performance status \leq 2, and have adequate organ function. In addition, subjects must have available relapsed and/or diagnostic formalin-fixed paraffin-embedded (FFPE) tumor

block or slide samples with successful identification of malignant clone sequences by the MRD assay at a central laboratory. Finally, subjects must have an MRD plasma sample collected ≤ 3 weeks **after** the post aHSCT PET-CT scan. During the run-in period, enrolled subjects will be monitored for MRD status; MRD-positive subjects who are PET-CT negative and meet other part 2 eligibility criteria will be assigned to treatment with blinatumomab.

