6.3.1 Dexamethasone Premedication

Mandatory premedication with dexamethasone is required before the treatment cycle and at each dose-step for the prevention of CRS and neurologic events resulting from blinatumomab treatment. Dexamethasone premedication will also be required before restarting blinatumomab after a dose interruption due to an adverse event or technical/logistical issue. Refer to [Table 2](#) for details. Collect dose, unit, frequency, route, start date, stop date and reason for dose change.

Table 2. Dexamethasone Pre-dose Treatment and for Events

Treatment Phase	Target Subjects	Dexamethasone Dose
Pre-dose dexamethasone prior to blinatumomab treatment cycle and before each dose-step increase	All subjects assigned to treatment	Dexamethasone 20 mg IV: within 1 hour prior to start of treatment in treatment cycle, and within 1 hour prior to dose-step increase.
Infusion interruption/dose modification due to adverse event or interruption due to technical/logistical event	Subjects who interrupt treatment > 4 hours	Dexamethasone 20 mg IV: within 1 hour prior to restart of treatment
In case of signs of CRS	Subjects with signs of CRS	Dexamethasone orally or IV at a dose maximum of 3 doses of 8 mg/day (24 mg/day) for up to 3 days. The dose should then be reduced step-wise over 4 days.
Infusion interruption/dose modification due to neurologic events	Subjects with neurologic event	Dexamethasone should be administered at a dose of at least 24 mg/day for up to 3 days. Dexamethasone will then be reduced step-wise over 4 days.

CRS = cytokine release syndrome; IV = intravenous

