3.1 Study Design

This is a phase 2, multicenter, open-label, single arm estimation study in adult subjects with high-risk DLBCL that are PET-CT negative post aHSCT. The study will consist of the following periods:

- Screening period (up to 28 days)
- Run-in period of up to 24 months to evaluate MRD status and assess eligibility for treatment assignment
- Treatment period of 12 weeks (which includes 8 weeks of treatment with blinatumomab followed by a 4-week treatment-free period)
- Safety follow-up visit 30 days after the last dose of blinatumomab
- Long-term follow-up period that begins after the safety follow-up visit is completed until 1 year from the first dose of blinatumomab.

The study will enroll approximately 90 subjects in the study with relapsed/refractory, biopsy-proven, high-risk DLBCL who are PET-CT negative at 90 days (\pm 30 days) post aHSCT (see Section 4.1 Part 1 Inclusion and Exclusion criteria of the protocol amendment 3 dated 18 July 2018).

During the run-in period, subjects will be followed by clinic visits at 3, 5, 7, and 9 months, and thereafter every 3 months (\pm 1 week) up to 24 months for monitoring of MRD status in plasma by next generation sequencing (NGS)-based assay. Subjects who remain MRD-negative by the end of the 24-month run-in period will end the study. It is expected that approximately 30 subjects will be MRD-positive either at screening or become MRD-positive during the 24-month run-in period.

The number of subjects enrolled may be altered in order to ensure that approximately 30 subjects are assigned to treatment with blinatumomab. Enrollment may be stopped once approximately 30 subjects have been assigned to treatment with blinatumomab. Subjects, who are MRD-positive at enrollment or become MRD-positive during the run-in period, and who meet all other part 2 eligibility criteria (see Section 4.2 Part 2 Inclusion and Exclusion criteria of the protocol amendment 3 dated 18 July 2018), will be assigned to treatment with blinatumomab.

Blinatumomab will be administered as a continuous intravenous (IV) infusion. Cycle 1 will be 12 weeks (84 days) in duration, which includes 8 weeks (56 days) of blinatumomab IV infusion followed by a 4-week (28 days) treatment-free interval.

Blinatumomab will be dosed at 9 µg/day for 7 days, followed by 28 µg/day for 7 days and 112 µg/day for 42 days.

[figure not shown]

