3.2 Sample Size

This is a single-arm estimation study. It is anticipated that an MRD negative rate of 10% could be observed by chance in this study. Therefore, if the observed rate of MRD negativity is at least 30%, then the sample size for this study ($N = 30$) is sufficient to demonstrate that, with 95% confidence, the rate of achieving MRD negativity is greater than 10%. This would also be sufficient to demonstrate evidence of clinical activity.

A table showing the exact binomial confidence intervals for different observed rates of MRD negativity with a sample size of $N = 30$ is presented below:

Table 3-1. Confidence Intervals for Different Observed Rates of MRD Negativity With a Sample Size of 30

Observed rate of MRD negativity, n (%)	Lower 95% Confidence Limit (%)	Upper 95% Confidence Limit (%)
8 (26.7)	12.3	45.9
9 (30.0)	14.7	49.4
11 (36.7)	19.9	56.1
12 (40.0)	22.7	59.4
14 (46.7)	28.3	65.7

The study will enroll approximately 90 subjects to achieve the desired sample size of 30 subjects who are MRD positive at the time of enrollment or during the run-in period. As part of the run-in period, subjects will be followed by clinic visits at 3, 5, 7, 9 and 12 months and thereafter every 3 months up to 24 months for monitoring of MRD status, thus it could be more than 30 subjects who at some point become MRD positive before the study ends. Any subject who becomes MRD positive after the first 30 subjects with treatment of blinatumomab will still be eligible for treatment and included in Full Analysis Set. Therefore the final sample size may be higher than 30 subjects.

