6.4 Pre-treatment Analysis Set

The pre-treatment analysis set will include all subjects that enroll in the study.

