9.1 General Considerations

Continuous variables will be summarized by the non-missing sample size (n), mean, standard deviation, median, first and third quartiles, minimum, and maximum.

Categorical variables will be summarized by the n and percentage in each category.

Point estimates for binomial proportions (eg., the primary efficacy endpoint) will be accompanied by 2-sided exact binomial 95% confidence intervals

([Clopper and Pearson, 1934](#)). Time to event endpoints will be summarized with Kaplan-Meier (KM) curves, KM proportions at selected time points, KM quartiles (when estimable), the number of subjects with events, the number of subjects censored, and the pattern of censoring. Point estimates of KM quartiles

([Brookmeyer and Crowley, 1982](#)) and KM proportions ([Kalbfleisch and Prentice, 1980](#)) will be accompanied by 2-sided 95% confidence intervals.

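### SAP 9.6.9 summarises dexamethasone premedication over all enrolled subjects, although only subjects assigned to treatment can receive it

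*SAP*

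**What the plan says.** SAP 9.6.9 contains one sentence: "Descriptive statistics will be produced to describe the required pre-medication (dexamethasone) exposure in the pre-treatment analysis set". The set it names is defined in SAP 6.4: "The pre-treatment analysis set will include all subjects that enroll in the study". Protocol 10.1.2.4 defines it the same way.

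The drug being summarised goes to a smaller group. In Protocol 6.3.1, Table 2, the target group for pre-dose dexamethasone is "All subjects assigned to treatment", and the schedule is "Dexamethasone 20 mg IV: within 1 hour prior to start of treatment in treatment cycle, and within 1 hour prior to dose-step increase". The Protocol Synopsis gives the planned sizes of the two groups: "Approximately 90 subjects will be enrolled in the study and approximately 30 subjects will be assigned to treatment with blinatumomab". SAP 3.2 adds, on the treated number: "Therefore the final sample size may be higher than 30 subjects".

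Many enrolled subjects are expected to leave without blinatumomab. SAP 3.1 says: "Subjects who remain MRD-negative by the end of the 24-month run-in period will end the study". Protocol sections 5 and 7.2.3 also end the study for subjects who fail the Part 2 criteria.

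Elsewhere the SAP uses treated-only sets for this kind of summary. SAP 6.6 assigns safety endpoints to the Primary Analysis Set at the primary analysis and to the Full Analysis Set at the final analysis. Both contain only subjects who received blinatumomab (SAP 6.1 and 6.2). The sections on either side of 9.6.9, blinatumomab exposure (9.6.8) and concomitant medication (9.6.10), use the Full Analysis Set.

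**The concern.** The analysis set does not match the population that can have the exposure. At the planned numbers, about two-thirds of the named set can never receive the premedication, because they are never assigned to treatment.

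The all-enrolled set suits its other uses in the SAP, namely baseline characteristics (9.4) and MRD status before treatment (9.5.3). No reason is given for using it for a treatment-period drug. Table 9-4 has no dexamethasone row, so nothing else in the SAP overrides 9.6.9.

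What is at stake is how one table reads. Premedication is mandatory, and the protocol gives its purpose as preventing cytokine release syndrome (CRS) and neurologic events. A table with about a third of subjects exposed could be taken for poor compliance. It would also describe a different group from the adverse event tables beside it.

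The SAP does not say whether an untreated subject's dexamethasone dose is zero or missing. Two programmers following 9.6.9 could therefore produce different tables.

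**Working it through.** The documents give no dexamethasone exposure figure, so there is none to reproduce. The check compares denominators.

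**Inputs**
- Enrolled: N = 90 (Protocol Synopsis; Protocol 3.3; SAP 3.2).
- Assigned to treatment: t = 30 (same places).
- Scheduled premedication per subject: 20 mg before the start and before each dose-step (Protocol Table 2). There are two dose-steps, on days 8 and 15 (Protocol 6.2.1.1), so 20 × (1 + 2) = 60 mg. This applies to a subject who reaches both steps without interruption and is used only as an illustration.
- Full compliance is assumed.

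**Step 1: share of the named set that is never treated.** (N − t)/N = (90 − 30)/90 = 66.7%.

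**Step 2: percent exposed.** On treated subjects, 30/30 = 100%. On the named set, t/N = 30/90 = 33.3%. Dilution factor N/t = 3.0.

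**Step 3: mean dose, two ways of handling untreated subjects.**
- Counted as zero: 60 × 30/90 = 20 mg against 60 mg, factor 3.0. The median is 0 mg, because 60 of the 90 values are zero.
- Counted as missing: SAP 9.1 says "Continuous variables will be summarized by the non-missing sample size (n), mean, standard deviation, median, first and third quartiles, minimum, and maximum". Only the 30 treated subjects contribute, so the mean is 60 mg, factor 1.0.

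**Step 4: sensitivity to the numbers.** The documents allow more than 30 treated and allow enrolment to be altered, but give no other figures. The counts below other than 90 and 30 are assumptions.

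| Enrolled | Treated | Percent exposed | Zero-filled mean (mg) | Factor |
|---|---|---|---|---|
| 90 | 30 | 33.3 | 20.0 | 3.0 |
| 90 | 36 | 40.0 | 24.0 | 2.5 |
| 90 | 40 | 44.4 | 26.7 | 2.25 |
| 90 | 45 | 50.0 | 30.0 | 2.0 |
| 80 | 30 | 37.5 | 22.5 | 2.67 |
| 100 | 30 | 30.0 | 18.0 | 3.33 |

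In every row the mean on non-missing values stays at 60 mg.

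**The case against.** A reader might infer that the plan understates dexamethasone exposure threefold across the board. The documents do not support that, for three reasons.

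- **Dose summaries.** SAP 9.1 bases continuous summaries on non-missing values. An untreated subject would normally have no premedication record, and nothing in the SAP says to enter a zero. Under that rule the mean and median do not move.
- **Percent exposed.** SAP 9.6.9 promises only descriptive statistics. It does not specify a percent-exposed row, whereas 9.6.8 and 9.6.10 do commit to proportions of subjects.
- **The figures.** Three is the ratio at the planned numbers and falls if more of the 90 are treated. The 60 mg is a schedule, not an expected mean: Table 2 adds a dose before a restart after an interruption of more than 4 hours, and early discontinuation removes doses.

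A reader might also infer that the interpretation of CRS or neurologic events is compromised. No planned analysis relates dexamethasone to those events, and steroids given to treat them are separate rows of Table 2, outside the required premedication that 9.6.9 covers. SAP 9.2 tabulates how many subjects received blinatumomab, so the treated denominator can be recovered. SAP 6.6 also shows the general intent.

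These points limit the consequence but leave the mismatch. SAP 6.6 does not expressly override the set named in 9.6.9, and any percentage computed as written would have the wrong denominator.

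Two smaller points stand. Table 9-4 names a Final Analysis Set that section 6 does not define; it probably means the Full Analysis Set. Also, dexamethasone is given up to an hour before the infusion, so a subject could be premedicated, never infused, and fall outside the Full Analysis Set. That calls for a listing, not for a denominator of about 90.

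**Conclusion.** The point holds as a wrong analysis set in one sentence of the SAP. Followed as written, 9.6.9 places a treatment-period drug in a set of about 90, of whom about 30 are planned to receive it. This is out of line with 6.6, 9.6.8 and 9.6.10.

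The size depends on what the table shows. At 90 enrolled and 30 treated, with full compliance, a percent-exposed row would show 33% instead of 100%. A mean with untreated subjects at zero would show 20 mg instead of the scheduled 60 mg. Dose summaries on non-missing values would be unaffected. An unconditional statement that exposure is understated threefold goes further than the text allows.

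The effect is confined to a descriptive safety table. The primary and secondary endpoints, the sample size and the DLT stopping rule do not depend on it. It is a minor correction that is worth making before the tables are programmed.

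**What to change.** In SAP 9.6.9, replace the pre-treatment analysis set with the Primary Analysis Set at the primary analysis and the Full Analysis Set at the final analysis, and state the denominator for any percentage. List separately any subject who received premedication but was never infused.

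The cost is one phrase and one short sentence in the SAP. No new data are needed, and no dosing, schedule or clinical rule changes.

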9.6.10 Exposure to Concomitant Medication

The number and proportion of subjects receiving concomitant medications from enrolment through the day before the first dose of blinatumomab (run-in period) and from day 1 through safety follow-up will be summarized by preferred term as coded by the World Health Organization Drug dictionary in the Full Analysis Set. In addition, the number and proportion of subjects receiving anticancer therapies during long term follow-up will be summarized by World Health Organization Drug dictionary preferred term in the Full Analysis Set.

9.7 Other Analyses

Not applicable

9.7.1 Analyses of Pharmacokinetic or Pharmacokinetic/Pharmacodynamic Endpoints

Not Applicable

9.7.2 Analyses of Clinical Outcome Assessments

Not Applicable

9.7.3 Analyses of Health Economic Endpoints

Not Applicable

9.7.4 Analyses of Biomarker Endpoints

Exploratory analyses may be performed on the MRD data. If the analyses will be performed then a separate biomarker supplemental analysis plan will be generated.

10. Changes From Protocol-specified Analyses

There are no changes to the protocol-specified analyses.

11. Literature Citations / References

Brookmeyer, R. and Crowley, J. A Confidence Interval for the Median Survival Time. *Biometrics*. 1982; 38:29-41.

Clopper CJ and Pearson ES. The Use of Confidence or Fiducial Limits Illustrated in the Case of the Binomial, *Biometrika*. 1934;26:404-413.

Kalbfleisch, J. D. and Prentice, R. L. The Statistical Analysis of Failure Time Data. New York: John Wiley & Sons; 1980.

12. Prioritization of Analyses

Not Applicable

13. Data Not Covered by This Plan

Not Applicable

14. Appendices

Appendix A. Reference Values/Toxicity Grades

Safety Laboratory Data

Treatment emergent laboratory abnormalities are defined as those which occur between the start of the first infusion of blinatumomab and the end of the treatment period.

Safety laboratory values below a distinct limit (eg, detection limit, documented as “< [limit]”) will be substituted by half of the limit and values above a distinct limit (documented as “> [limit]”) will be substituted by the limit itself for all analyses.

Grading (based on CTCAE version 4.03 or above) will be assigned to each laboratory result as detailed in [Table 14-1](#). Depending on the toxicity definition, the same result may be assigned to two gradings for deviations towards higher or lower values. In case no lower limit of normal is provided for the absolute lymphocyte, neutrophils or leukocyte counts, it will not be differentiated between grade 1 and grade 0 results for these parameters. Values not meeting any of the criteria will be assigned a grade 0.

Table 14-1. Grading of Selected Laboratory Parameters

Laboratory Parameter [Unit]	Grade 1	Grade 2	Grade 3	Grade 4
Lymphocytes [G/L]	0.8 - < LLN	0.5 - < 0.8	0.2 - < 0.5	< 0.2
Neutrophils [G/L]	1.5 - < LLN	1.0 - < 1.5	0.5 - < 1.0	< 0.5
Leukocytes [G/L]	3.0 - < LLN	2.0 - < 3.0	1.0 - < 2.0	< 1.0
Platelets [G/L]	75 - < LLN	50 - < 75	25 - < 50	< 25
Hemoglobin [g/L]*	100 - < LLN	80 - < 100	65 - < 80	< 65
Albumin [g/L]	30 - < LLN	20 - < 30	< 20	not defined
AST*	> ULN – 3*ULN	> 3*ULN – 5*ULN	> 5*ULN – 20*ULN	> 20*ULN
ALT *	> ULN – 3*ULN	> 3*ULN – 5*ULN	> 5*ULN – 20*ULN	> 20*ULN
GGT	> ULN – 2.5*ULN	>2.5*ULN – 5*ULN	> 5*ULN – 20*ULN	> 20*ULN
Bilirubin	> ULN – 1.5*ULN	>1.5*ULN – 3*ULN	> 3*ULN – 10*ULN	> 10*ULN
Fibrinogen^	%change of BL <25% or 0.75*LLN - < LLN	25%- <50% of BL or < 75*LLN – 0.5*LLN	50% - <75% of BL or < 0.5* LLN – 0.25*LLN	>= 75% of BL or < 50mg/dL or < 0.25*LLN

Page 1 of 2

Footnotes defined on the next page of the table

Table 14-1. Grading of Selected Laboratory Parameters

Laboratory Parameter [Unit]	Grade 1	Grade 2	Grade 3	Grade 4
Corrected Calcium [mmol/L]*	2.0 - < LLN	1.75 - < 2.0	1.5 - < 1.75	< 1.5
Potassium [mmol/L]*	not defined	3.0 - < LLN	2.5 - < 3.0	< 2.5
Lipase	> ULN – 1.5*ULN	> 1.5*ULN – 2.0*ULN	> 2.0*ULN – 5.0*ULN	> 5.0*ULN
Amylase	> ULN – 1.5*ULN	> 1.5*ULN – 2.0*ULN	> 2.0*ULN – 5.0*ULN	> 5.0*ULN

Page 2 of 2

BL: baseline value, LLN: Lower limit of normal, ULN: Upper limit of normal

*: Clinical criteria from CTC AE 4.0 grading were not considered in order to assign grades

^: In case of conflicting criteria the higher grade will be assigned, % change only used when baseline is <LLN

For more details refer The **Common Terminology Criteria for Adverse Events (CTCAE)**, version 4.03 which is available at the following location:

https://evs.nci.nih.gov/ftp1/CTCAE/CTCAE_4.03_2010-06-14_QuickReference_8.5x11.pdf

Notable values for vital signs are defined according to the following table

Table 14-2. Notable Abnormalities of Vital Signs

Vital Signs	Notable Abnormalities
Pulse rate (bpm)	>120 <50
Blood pressure (mmHg)	Systolic ≥160 ≤90 Diastolic ≥105 ≤50
Weight (kg)	change from baseline ≥10% (in both directions)
Body temperature (°C)	> 39

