AST/ALT	> 8 x ULN at any time > 5 x ULN but < 8 x ULN for ≥ 2 weeks > 5 x ULN but < 8 x ULN and unable to adhere to enhanced monitoring schedule > 3 x ULN with clinical signs or symptoms that are consistent with hepatitis (such as right upper quadrant pain/tenderness, fever, nausea, vomiting, jaundice).	In the presence of no important alternative causes for elevated AST/ALT and/or TBL values > 3 x ULN (when baseline was < ULN)
	OR	
ALP	> 8 x ULN at any time	--

ALP = alkaline phosphatase; ALT = alanine aminotransferase; AST = aspartate aminotransferase; INR = international normalized ratio; TBL = total bilirubin; ULN = upper limit of normal

6.4.2 Criteria for Rechallenge of Amgen Investigational Product and Other Protocol-required Therapies After Potential Hepatotoxicity

If signs or symptoms recur with rechallenge, then blinatumomab and other protocol-required therapies, as appropriate should be permanently discontinued.

Subjects who clearly meet the criteria for permanent discontinuation (as described in [Table 3](#)) should never be rechallenged.

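### SAP Table 14-1 has no cut-offs for at least 5 of the 16 laboratory items in SAP 9.6.3 and grades the others in one direction only, so the grade 0 default could misgrade their shifts

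*SAP*

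**What the plan says.** SAP 9.6.3 first states that summary statistics for actual values and "changes from baseline of laboratory parameters listed below will be presented". It then says that "shift tables will be summarized with toxicity grades using CTCAE by worst on-study increase and decrease values", and the numbered list of 16 items follows. Item 5 is "Alkaline phosphatase" and item 16 is "Creatinine increased". The section does not say which table or which CTCAE version supplies the grades.

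The grading procedure is in SAP Appendix A: "Grading (based on CTCAE version 4.03 or above) will be assigned to each laboratory result as detailed in" Table 14-1. The same paragraph expects two-sided grading, since "the same result may be assigned to two gradings for deviations towards higher or lower values", and it closes with the default: "Values not meeting any of the criteria will be assigned a grade 0". Table 14-1 has 15 rows and is titled as covering selected parameters. A note below it refers the reader to CTCAE 4.03 for more detail.

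**The concern.** A programmer needs one rule that gives a grade for each listed item in each requested direction. Section 9.6.3 points to CTCAE in general. Appendix A points to a table that omits several of the listed items, and it then supplies a default that turns the omission into a grade of zero. A missing row would therefore not show up as missing. It would appear in the output as absence of toxicity.

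Safety is a secondary objective of this single-arm trial, and protocol 10.4.4.3 names liver parameters among the safety laboratory analyses. Alkaline phosphatase is one of the analytes in the hepatotoxicity rules of protocol 6.4.1 (Table 3), where the withholding entry is "> 8 x ULN at any time". Under a literal reading of SAP Appendix A, a value that high would sit in the shift table as grade 0. Creatinine is in the same position, although its entry in the list is worded as a direction of change, which suggests that a graded increase is meant.

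**Working it through.** The plan gives no figure to reproduce. The check compares the 16 items in SAP 9.6.3 with the 15 rows of Table 14-1 and notes the direction of each row's cut-offs.

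| Items in SAP 9.6.3 | Row in Table 14-1 | Cut-offs |
|---|---|---|
| Corrected calcium, hemoglobin, platelets, neutrophils, lymphocytes | yes | low side only |
| Total bilirubin, AST, ALT, amylase, lipase | yes | high side only |
| Direct bilirubin | only if the Bilirubin row is meant to cover it | high side only |
| Magnesium, alkaline phosphatase, LDH, immunoglobulins, creatinine | no | none |

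**Count without a row.** If Bilirubin covers direct bilirubin, 16 − 11 = 5 items have no row, and 5/16 = 31%. If it means total bilirubin only, 16 − 10 = 6, and 6/16 = 37.5%. Immunoglobulins count as one item here, although that item holds IgG, IgA and IgM.

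**Direction.** Of the items with a row, 5 have low-side cut-offs only and 5 (or 6 with direct bilirubin) have high-side cut-offs only. None has both, although 9.6.3 asks for increase and decrease and Appendix A foresees two gradings of one result.

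**Rows the list does not use.** Ten rows serve the list, so 15 − 10 = 5 do not: leukocytes, albumin, GGT, fibrinogen and potassium. GGT is not among the analytes in protocol Table 5.

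**Applying the rule literally.** An alkaline phosphatase or creatinine result is a laboratory result, it meets no criterion in Table 14-1, and it becomes grade 0 whatever its value. A high calcium has a row, but that row runs from below the lower limit of normal down to below 1.5 mmol/L. The high value meets none of those criteria and also becomes grade 0. The calcium case does not depend on how an absent row is read.

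**CTCAE version.** Appendix A of the SAP allows 4.03 or above, the note under Table 14-1 cites 4.03, and the protocol (9.2.2.1 and its Appendix A) cites 4.0. The fallback to CTCAE is therefore not tied to one version.

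**The case against.** The strongest reply is that Table 14-1 was never meant to be the whole grading source. Section 9.6.3 says CTCAE and does not cite Table 14-1, whereas 9.6.4 and 9.6.5 do cite Table 14-2. The table is titled as a selection, and the note below it points to CTCAE 4.03. The grade 0 sentence closes a paragraph about applying row criteria, so it can be read as covering only parameters that have a row. The reference to the list also sits in the summary-statistics sentence, and both protocol 10.4.4.3 and SAP Table 9-4 limit shift tables to selected parameters.

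Much of this stands, and it is why the consequence is worded as what could happen under literal application. It does not settle the matter. The note offers more detail and does not say that full CTCAE governs where a row is missing. No text defines the selection. If the selection were the rows of Table 14-1, it would include GGT, which is not collected, and leave out creatinine. Two programmers could follow the SAP faithfully and produce different tables.

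A reader might infer that renal and alkaline phosphatase toxicity would be hidden from the safety report whatever happens. The documents do not support that. Protocol 9.2.2.1 requires all grade 3 and 4 laboratory values to be recorded as adverse events, and SAP 9.6.2 tabulates treatment-emergent events by worst grade. SAP 9.6.3 also summarises actual values and changes from baseline for every listed item. The hepatotoxicity rules in the protocol work on multiples of the upper limit of normal and do not use the SAP grades. What remains is that the blanket recording rule does not reach grades 1 and 2, and that an adverse event table could show a grade 3 value where the shift table shows grade 0.

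A reader might also take the fibrinogen grade 2 limit, printed as 75 times the lower limit of normal, to mean that normal values would be graded 2. The neighbouring limits of 0.75 and 0.5 times the lower limit make a misprint the natural explanation, and a character may have been lost in reading the PDF. Fibrinogen is not on the 9.6.3 list, so no shift table for a listed item is affected.

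**Conclusion.** The point holds at low severity. The list in SAP 9.6.3 and the grading table in Appendix A do not match: 5 of 16 items have no cut-offs (6 if direct bilirubin is not covered), and every row that serves the list is one-sided. Combined with the grade 0 default as stated, this could yield shift tables showing only grade 0 for creatinine, alkaline phosphatase and calcium increases. That would contradict the instruction in 9.6.3 to grade by CTCAE.

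The size of the effect assumes that Appendix A is programmed literally and that the 16 items are the ones to be shifted. On the narrower reading of the default, items without a row are left without a stated rule instead of being set to grade 0, but the missing directions, such as high calcium, are still set to grade 0. The documents do not show which of the missing items and directions CTCAE itself grades, so the number of shifts that would actually be misgraded cannot be given from them.

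**What to change.** Make four changes in the SAP:

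1. In 9.6.3, cite the grading source for the shift tables and state which items are shifted.
2. State that full CTCAE, at one fixed version, applies to any listed parameter or direction with no cut-off in Table 14-1, or add those rows and directions to the table.
3. Limit the grade 0 default to parameters and directions that have criteria.
4. Show any listed item for which CTCAE gives no grades as low, normal or high against the reference range. State whether the Bilirubin row covers direct bilirubin.

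As minor clean-up, check the fibrinogen grade 2 limit against the 0.75 times lower limit of normal in the grade 1 cell, and remove the GGT row.

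The cost is an edit to SAP 9.6.3 and Appendix A and to the programming specification. No new data are needed, because protocol Table 5 already lists all the analytes concerned.
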